11.5.3 Pharmacokinetics

Analysis will be performed under PK analysis set.

LML134 plasma concentration data will be listed by treatment, subject, and visit/sampling time point. Descriptive summary statistics will be provided by treatment and visit/sampling time point, including the frequency (n, %) of concentrations below the LLOQ and reported as zero.

Conventional PK parameters will not be calculated due to the limited sampling schedule. However, plasma concentrations will be listed and summary statistics for concentrations will be provided for plasma. The data will be part of the over-all Population PK model.

Concentrations below the LLOQ will be treated as zero in summary statistics for concentration data only. They will not be considered for calculation of PK Parameters (with the exception of the pre-dose samples).

11.5.4 Pharmacokinetic / pharmacodynamic interactions

Not applicable.

11.5.5 Other assessments

Not applicable.

Corporate Confidential Information

Corpor
ate

11.7 Sample size calculation

It is planned to have data for 36 subjects with evaluable results under the primary endpoint without any major protocol deviations. Assuming a 20% drop-out rate we expect to enroll approximately 46 subjects. In case there will be less than 36 evaluable subjects additional subjects may be enrolled.

Based on [Czeisler et al 2005](#) a 2 minute increase in primary endpoint for SWD patients compared to placebo is considered to be the ‘true effect’. Furthermore a SD of 4 minutes and a 20% drop out rate is used based on other sleep disorder study experience.

Efficacy criteria:

- a. Statistical significance: A significant increase compared to placebo in sleep latency characterized by p-value < 0.1

And

- b. At least 1 minute increase in MSLT sleep latency compared to placebo characterized by an estimated mean difference of > 1 minute

Sample size is evaluated based on a simulation exercise with an ANOVA model with treatment and period as fixed effects. The following operating characteristics are observed:

Table 11-1 Operating characteristics for dual criteria

True effect* (in mins)	Both criteria met (%)	Both criteria failed (%)	One of the criteria met (%)
1.0	41.3	50.0	8.7
1.2	49.7	41.6	8.7
1.5	62.2	29.8	8.0
1.7	69.9	22.9	7.2
2.0	80.0	14.4	5.6
2.2	85.4	10.2	4.5
2.5	91.5	5.6	2.9

* True effect: Change in MSLT (LML134X-Placebo)

Futility Analysis:

An interim analysis is planned at mid-way with 18 completers to evaluate the chance of attaining proof of concept at the end of the trial. A very low chance may result in early stoppage of the trial due to futility.

11.8 Power for analysis of key secondary variables

No power analysis was performed for secondary variables.

12 Ethical considerations

12.1 Regulatory and ethical compliance

This clinical study was designed and shall be implemented, executed and reported in accordance with the ICH Harmonized Tripartite Guidelines for Good Clinical Practice, with applicable local regulations (including European Directive 2001/20/EC, US Code of Federal Regulations Title 21, and Japanese Ministry of Health, Labor, and Welfare), and with the ethical principles laid down in the Declaration of Helsinki.

12.2 Responsibilities of the investigator and IRB/IEC

Before initiating a trial, the investigator/institution must obtain approval/favorable opinion from the Institutional Review Board/Independent Ethics Committee (IRB/IEC) for the trial protocol, written informed consent form, consent form updates, subject recruitment procedures (e.g. advertisements) and any other written information to be provided to subjects. Prior to study start, the investigator is required to sign a protocol signature page confirming his/her agreement to conduct the study in accordance with these documents and all of the instructions and procedures found in this protocol and to give access to all relevant data and records to Novartis monitors, auditors, Novartis Quality Assurance representatives, designated agents of Novartis, IRBs/IECs, and regulatory authorities as required. If an inspection of the clinical site is requested by a regulatory authority, the investigator must inform Novartis immediately that this request has been made.

For multi-center trials, a Coordinating Investigator will be selected by Novartis by the time of Last Patient Last Visit to be a reviewer and signatory for the clinical study report.

12.3 Publication of study protocol and results

The key design elements of this protocol will be posted in a publicly accessible database such as clinicaltrials.gov. In addition, upon study completion and finalization of the study report the results of this trial will be either submitted for publication and/or posted in a publicly accessible database of clinical trial results.

12.4 Quality Control and Quality Assurance

Novartis maintains a robust Quality Management (QM) system that includes all activities involved in quality assurance and quality control, including the assignment of roles and responsibilities, the reporting of results, and the documentation of actions and escalation of issues identified during the review of quality metrics, incidents, audits and inspections.

Audits of investigator sites, vendors, and Novartis systems are performed or overseen by Novartis Pharma Auditing and Compliance Quality Assurance (or CRO working on behalf of Novartis), a group independent from those involved in conducting, monitoring or performing quality control of the clinical trial. The clinical audit process uses a knowledge/risk based approach.

Audits are conducted to assess GCP compliance with global and local regulatory requirements, protocols and internal SOPs, and are performed according to written Novartis processes.

13 Protocol adherence

This protocol defines the study objectives, the study procedures and the data to be collected on study participants. Additional assessments required to ensure safety of subjects should be administered as deemed necessary on a case by case basis. Under no circumstances is an investigator allowed to collect additional data or conduct any additional procedures for any research related purpose involving any investigational drugs under the protocol.

Investigators ascertain they will apply due diligence to avoid protocol deviations. If an investigator feels a protocol deviation would improve the conduct of the study this must be considered a protocol amendment, and unless such an amendment is agreed upon by Novartis and approved by the IRB/IEC and health authorities, where required, it cannot be implemented.


15 Appendix 1: Liver Event Definitions and Follow-up Requirements

Table 15-1 Liver Event Definitions

Definition	Thresholds
Potential Hy's law cases	
 ALT or AST > 3 × ULN and TBL > 2 × ULN without initial increase in ALP to > 2 × ULN
ALT or AST elevation with coagulopathy	
 ALT or AST > 3 × ULN and INR > 1.5 (in the absence of anticoagulation)
ALT or AST elevation accompanied by symptoms	
 ALT or AST > 3 × ULN accompanied by (general) malaise, fatigue, abdominal pain, nausea, or vomiting, or rash, or eosinophilia
Isolated ALT or AST elevation	
 ALT or AST > 8 × ULN 5 × ULN < ALT/AST ≤ 8 × ULN 3 × ULN < ALT/AST ≤ 5 × ULN
Isolated ALP elevation	
 ALP > 2 × ULN (in the absence of known bone pathology)
Others	
 Any clinical event of jaundice (or equivalent term) Any adverse event potentially indicative of liver toxicity

Table 15-2 Actions required for Liver Events

Criteria	Actions required
Potential Hy's Law case ALT or AST elevation with coagulopathy ALT or AST elevation accompanied by symptoms Isolated ALT or AST elevation > 8 × ULN Jaundice	
 Discontinue the study treatment immediately Hospitalize, if clinically appropriate Establish causality Complete CRFs per liver event guidance*
Isolated ALT or AST elevation > 5 to ≤ 8 × ULN	
 If confirmed, consider interruption or discontinuation of study drug If elevation persists for more than 2 weeks, discontinue the study drug Establish causality Complete CRFs per liver event guidance*
Isolated ALT or AST elevation > 3 to ≤ 5 × ULN (patient is asymptomatic)	
 Monitor liver chemistry tests two or three times weekly
Isolated ALP elevation	
 Repeat liver chemistry tests within 48-72 hours If elevation is confirmed, measure fractionated ALP; if >50% is of liver origin, establish hepatic causality Complete CRFs per liver event guidance*

Criteria	Actions required
Any AE potentially indicative of liver toxicity	
 • Consider study treatment interruption or discontinuation • Hospitalize if clinically appropriate • Complete CRFs per liver event guidance*

*Liver event guidance for CRF completion is available in the Site Operations Manual

Table 15-3 Exclusion of underlying liver disease

Disease	Assessment
Hepatitis A, B, C, E	
 • IgM anti-HAV; HBSAg, IgM anti-HBc, HBV DNA; anti-HCV, HCV RNA, IgM & IgG anti-HEV, HEV RNA
CMV, HSV, EBV infection	
 • IgM & IgG anti-CMV, IgM & IgG anti-HSV; IgM & IgG anti-EBV
Autoimmune hepatitis	
 • ANA & ASMA titers, total IgM, IgG, IgE, IgA
Alcoholic hepatitis	
 • Ethanol history, GGT, MCV, CD-transferrin
Nonalcoholic steatohepatitis	
 • Ultrasound or MRI
Hypoxic/ischemic hepatopathy	
 • Medical history: acute or chronic CHF, hypotension, hypoxia, hepatic venous occlusion. Ultrasound or MRI.
Biliary tract disease	
 • Ultrasound or MRI, ERCP as appropriate.
Wilson disease	
 • Caeruloplasmin
Hemochromatosis	
 • Ferritin, transferrin
Alpha-1-antitrypsin deficiency	
 • Alpha-1-antitrypsin

16 Appendix 2: Specific Renal Alert Criteria and Actions

Table 16-1 Specific Renal Alert Criteria and Actions

Criteria	Action required
Serum creatinine (sCr) increase 25 – 49% compared to baseline	
 Consider causes and possible interventions Follow up within 2-5 days
Serum creatinine increase > 50%	
 Consider causes and possible interventions Repeat assessment within 24-48h if possible Consider drug interruption or discontinuation unless other causes are diagnosed and corrected Consider hospitalization and specialized treatment
Protein-creatinine or albumin-creatinine ratio increase \geq 2-fold or new onset dipstick proteinuria \geq 1+ or Albumin-creatinine ratio (ACR) \geq 30 mg/g or \geq 3 mg/mmol; or Protein-creatinine ratio (PCR) \geq 150 mg/g or >15 mg/mmol	
 Consider causes and possible interventions Assess serum albumin & serum protein Repeat assessment to confirm Consider drug interruption or discontinuation unless other causes are diagnosed and corrected
New onset glucosuria on urine dipstick (unless related to concomitant treatment, diabetes)	
Assess & document:
 
 Blood glucose (fasting) Serum creatinine Urine albumin-creatinine ratio
New hematuria on dipstick	
Assess & document:
 
 Urine sediment microscopy Assess sCr and urine albumin-creatinine ratio Exclude infection, trauma, bleeding from the distal urinary tract/bladder, menstruation Consider bleeding disorder

Additional specialized assessments are available to assess renal function or renal pathology. (Note: In exceptional cases when a nephrologist considers a renal biopsy, it is strongly recommended to make specimen slides available for evaluation by Novartis to potentially identify project-wide patterns of nephrotoxicity.)

Whenever a renal event is identified, a detailed subject history and examination are indicated to identify, document and potentially eliminate risk factors that may have initiated or contributed to the event:

- Blood pressure assessment (after 5 min rest, with an appropriate cuff size)
- Signs and symptoms such as fever, headache, shortness of breath, back or abdominal pain, dysuria, hematuria, dependent or periorbital edema
- Changes in blood pressure, body weight, fluid intake, voiding pattern, or urine output
- Concomitant events or procedures such as trauma, surgical procedures, cardiac or hepatic failure, contrast media or other known nephrotoxin administration, or other potential causes of renal dysfunction, e.g., dehydration, hemorrhage, tumor lysis

Table 16-2 Follow-up of renal events

Action	Follow up
Assess*, document and record in the Case Report Form (CRF) or via electronic data load. Review and record possible contributing factors to the renal event (co-medications, other co-morbid conditions) and additional diagnostic procedures (MRI etc) in the CRF.	
 • Urine dipstick and sediment microscopy • Blood pressure and body weight • Serum creatinine, electrolytes (sodium, potassium, phosphate, calcium), bicarbonate and uric acid • Urine output
Monitor subject regularly (frequency at investigator's discretion) until:	
 • Event resolution: (sCr within 10% of baseline or protein-creatinine ratio within 50% of baseline) 
or
 
 • Event stabilization: sCr level with $\pm 10\%$ variability over last 6 months or protein-creatinine ratio stabilization at a new level with $\pm 50\%$ variability over last 6 months.

* Urine osmolality: in the absence of diuretics or chronic kidney disease this can be a very sensitive metric for integrated kidney function that requires excellent tubular function. A high urinary osmolality in the setting of an increase in sCr will point toward a “pre-renal” cause rather than tubular toxicity.

1.1 Scope of document

The RAP documents contain detailed information to aid the production of Statistics & Programming input into the Clinical Study Report (CSR) for trial “**CLML134X2201**”.

The Statistical analysis plan (SAP) describes the implementation of the statistical analysis planned in the protocol.

1.2 Study reference documentation

A study protocol (v04) is available at the time of finalization of Statistical Analysis Plan.

Corporate Confidential Information

1.3 Study objectives

1.3.1. Primary objective(s)

Primary objective(s)	Endpoints related to primary objectives

 To demonstrate that wakefulness in SWD patients is significantly increased after treatment with LML134 compared to placebo 	
 Average sleep latency over two consecutive test nights as measured by the MSLT

1.3.2. Secondary objective(s)

Secondary objective(s)	Endpoints related to secondary objective(s)

 To assess the safety and tolerability of LML134 compared to placebo in SWD patients 	
 Standard safety assessments such as vital signs, ECG, hematology, blood chemistry, urinalysis, AE reporting, and daytime PSG to assess drug effect on sleep

 To assess the plasma pharmacokinetics of LML134 in SWD patients 	
 Due to sparse sampling, only plasma concentrations will be listed and no PK parameter will be evaluated by noncompartmental analysis. The data will be part of the overall Population PK model

 To evaluate the time course of LML134 effect on wakefulness compared to placebo 	
 MSLT at each time point averaged over two consecutive test nights

[figure not shown]
1.4 Study design and treatment

This is a randomized, subject and investigator-blinded, placebo controlled, crossover, multi-center Proof of Concept (PoC) study with in-house simulated laboratory night shifts in patients with SWD.

This non-confirmatory study will include two treatment arms: LML134 and placebo. The study will utilize a 2x2 crossover design, with two treatment periods and two sequences as shown in [Figure 1-1](#) whereas assessment details are shown in [Figure 1-2](#).

Approximately 46 subjects were planned to be randomized in this study (to achieve 36 completers). All subjects will receive both treatments (LML134 and placebo), one in each treatment period, with the order of treatment being randomized. The study is prematurely terminated based on business decision after 18 completers.

Figure 1-1 Study Design

2 First interpretable results (FIR)

No first interpretable result (FIR) is planned for this study. All the results will be represented in clinical study report (CSR).

4 Statistical methods: Analysis sets

For all analysis sets, subjects will be analysed according to the actual study treatment(s) received. This is due to fact that it is known that a few subjects has been mis-randomized to a different treatment group as compared to the planned list of randomization. In order to make use of full data , all analysis will be performed on actual treatment group received by subject instead of a planned one.

The full analysis set will include all subjects that received any study drug and had any post-baseline assessment.

The safety analysis set will include all subjects that received any study drug.

The PK analysis set will include all subjects with at least one available valid (i.e. not flagged for exclusion) PK concentration measurement, who received any study drug and with no protocol deviations that impact on PK data.

For subjects for which the actual treatment received does not match the randomized treatment the treatment actually received will be used for the analysis.

For subjects for which the actual sequence of treatments received does not match the randomized sequence of treatments, the actual sequence will be used for analysis involving a sequence component (e.g. ANOVAs with a sequence effect) if the actual sequence is one of the sequences planned in the study design. If the actual sequence is not one of the sequences planned in the study design, the randomized sequence will be used for analysis involving a sequence component but data points from periods in which the subject has not received the randomized treatment will be excluded from the analysis.

Types of analysis/endpoints	Analysis set to be used
Demographics and baseline characteristics	Full analysis set
Analysis of safety data	Safety set
Analysis of PK data	PK set

The analysis sets and protocol deviation codes are related as follows:

Table 4-1 Protocol deviation codes and analysis sets

Category Deviation code	Text description of deviation	Data exclusion
Subjects are excluded from PK analysis in case of these PDs:		Exclude subject from PK analysis set
Subjects are excluded from PD analysis in case of these PDs:		Exclude subject from PD analysis set

If updates to this table are needed, an amendment to the SAP needs to be implemented prior to DBL.

5 Statistical methods for Pharmacokinetic (PK) parameters

All subjects within the PK analysis set will be included in the PK data analysis.

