6.1.3 Statistical model, assumptions and hypotheses

MSLT from both periods will be included in the analysis.

Corporate Confidential Information

Due to high variability and time difference between screening MSLT and post treatment records, screening MSLT will not be used as a covariate for modelling. Total sleep time from sleep diary data during baseline will be used as baseline covariate. Therefore both smoking status (nicotine intake) and total sleep time at baseline will be considered as covariates in the model.

The primary variable, mean MSLT of a subject within a period, will be analyzed using a mixed effect analysis of variance model. This model will have the mean MSLT as the dependent variable; treatment, actual treatment sequence, smoking status at screening, total sleep time at baseline, treatment interaction with total sleep time at baseline and smoking status and period as fixed effects and a subject level random intercept. Primary analysis will be assessed over full analysis set.

Least square estimates for each treatment (LML134 and placebo) and treatment difference (LML134 vs placebo) along with 95% confidence interval will be reported.

The following assessments will be performed to judge efficacy of LML134:

1. Statistical significance: One sided (superiority) p-value of LML134 vs placebo from above fitted ANOVA model will be reported.

A p-value < 0.1 will be considered as a positive sign for statistical significance.

2. Estimate of treatment difference (LML134 vs Placebo) will be reported.
An estimate of treatment difference > 1 minute would be considered as significant.

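### Must the SAP restate Table 11-1's 80% chance of success now that the trial stopped at 18 completers, not 36?

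*SAP*

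**What the plan says.** Protocol 11.7 sets the target: "It is planned to have data for 36 subjects with evaluable results under the primary endpoint without any major protocol deviations". If the number falls short, more may be added: "In case there will be less than 36 evaluable subjects additional subjects may be enrolled". The design effect is 2 minutes, and on variability the section says: "Furthermore a SD of 4 minutes and a 20% drop out rate is used based on other sleep disorder study experience". It does not say whether that SD is within-subject or total. On method: "Sample size is evaluated based on a simulation exercise with an ANOVA model with treatment and period as fixed effects". The two criteria, p below 0.1 and an estimated difference above 1 minute, are joined by "And"-type wording, so both are required. Table 11-1 has separate columns for both met, both failed and one met. The same section also foresees a look at half size: "An interim analysis is planned at mid-way with 18 completers to evaluate the chance of attaining proof of concept".

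SAP 1.4 gives 36 completers as the plan and then states: "The study is prematurely terminated based on business decision after 18 completers". SAP 6.1.3 introduces the criteria with "The following assessments will be performed to judge efficacy of LML134". It keeps the one-sided p below 0.1 and the second rule, "An estimate of treatment difference > 1 minute would be considered as significant", and it reports the treatment difference with a 95% confidence interval. Parts of SAP 6.1.3, 6.1.3.1 and 6.1.3.3 are blacked out, and no Section 3 is visible.

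**The concern.** The only stated chance of success belongs to a trial with twice as many completers. The SAP was written with the stop already known, yet its visible text applies the two criteria unchanged. It gives no operating characteristics for 18 and no guidance on reading a missed or split result.

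The study is meant to inform whether development in this indication should continue. A reader who takes Table 11-1 at face value expects a drug with the assumed effect to miss the dual criterion 20% of the time. If the true figure is nearer 42%, a miss is much weaker evidence against the drug than it seems.

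**Working it through.** **Inputs.** From Protocol 11.7: 36 evaluable subjects, SD 4 minutes, true effect 2 minutes, p < 0.1, estimate > 1 minute. From Protocol 11.4.2: the p-value is one-sided. From SAP 1.4: 18 completers.

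**Step 1: reproduce the plan's figure.** Take SD 4 per observation with no within-subject correlation and a normal critical value of 1.2816.

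- SE = 4 × √(2/36) = 0.943.
- Estimate needed for p < 0.1: 1.2816 × 0.943 = 1.21 minutes. This exceeds 1, so it decides whether both criteria are met.
- Both met: Φ((2 − 1.21)/0.943) = 79.9%.
- Both failed: Φ((1 − 2)/0.943) = 14.4%.
- One met: 5.6%.

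Table 11-1 prints 80.0 / 14.4 / 5.6. All seven rows agree to within 0.1 point. A two-sided 0.1 test (68.3%), 46 subjects (86.8%), or 4 minutes as the SD of the paired difference at 36 (93.3%) does not fit. The table is therefore correct for 36.

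**Step 2: same model at 18.**

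- SE = 4 × √(2/18) = 1.333.
- Estimate needed for p < 0.1: 1.2816 × 1.333 = 1.71 minutes (1.78 with t on 16 df).
- Both met: Φ((2 − 1.71)/1.333) = 58.6%, or 57.9% with t on 33 df and 57.1% with t on 16 df.
- Both failed: Φ((1 − 2)/1.333) = 22.7%.
- One met: 18.7% (normal) to 20.2% (t, 16 df). Nearly all of this is an estimate above 1 minute with p ≥ 0.1.

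**Step 3: how far this depends on the undefined SD.** If 4 minutes is a within-subject SD, Step 2 stands. If it is a total SD with correlation ρ between a subject's two period scores, SE = 4 × √(2(1 − ρ)/n). The documents give no ρ, so the values below are assumptions (true effect 2; t on n − 2 df).

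| ρ | Both met, n = 36 | Both met, n = 18 | One met, n = 18 |
|---|---|---|---|
| 0 | 79.1% | 57.1% | 20.2% |
| 0.3 | 88.1% | 67.8% | 13.7% |
| 0.5 | 93.2% | 78.0% | 7.8% |
| 0.7 | 97.4% | 90.1% | 2.9% |

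At ρ = 0.5 and n = 18, SE = 4 × √(1/18) = 0.943, the same standard error that produced the printed 80%. The correlation at which 18 completers give 80% is 0.50 (normal) to 0.53 (t, 16 df).

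**Step 4: what the planned output already shows.** At SE 1.333 the 95% interval has half-width 2.12 × 1.333 = 2.83 minutes, against 1.92 at 36. An estimate of 1.5 would give a one-sided p of 0.14 and an interval from −1.3 to 4.3, visibly compatible with both 0 and 2. The chance of p < 0.1 at zero effect stays at 10%.

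**The case for a change.** The strongest case for acting is that power is lost whichever meaning the SD has: 7 to 22 points in the table above. The SAP was the natural place to say so, and one paragraph would cost almost nothing. The interval is reported, but efficacy is judged by the two criteria. One safeguard was also loosened: Protocol 11.4.5 commits to reporting the probabilities that the difference exceeds 0 and 1, while SAP 6.1.3.3 makes the Bayesian analysis optional.

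Much of this is true. The visible text gives no figure for 18, and the SD is not defined. But the points do not add up to a needed change.

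- A split result is not left open. Protocol 11.7 requires both criteria, so a split does not meet them.
- Running this analysis on about 18 completers was already foreseen for the interim look (Protocol 11.4.2 and 11.7), though for futility.
- Reading a miss against 0 adds nothing, because a one-sided p ≥ 0.1 always puts the lower 95% limit below 0. That a non-significant result is not proof of no effect is ordinary reporting practice.
- The Bayesian analysis was supportive only, and the criteria do not use it.
- Protocol 11.4.5 defers the interim decision criteria to the SAP. The blacked-out text could hold a statement about 18 completers, so its absence cannot be asserted for the whole plan.

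**Conclusion.** No change to the plan is needed. No figure in either document is wrong: 80.0% is correct for 36 evaluable subjects, the visible SAP does not claim it for 18, and SAP 1.4 gives both numbers.

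The chance of meeting both criteria at 18 is 57-59% under the table's no-correlation model, and about 68-90% if 4 minutes is a total SD with an assumed correlation of 0.3 to 0.7. The documents do not settle which applies. None of these is the power of the SAP's own model, which adds a subject intercept, sequence, covariates and interactions. The full analysis set may also hold more than 18 subjects: if 20 to 24 (assumed) had both periods, 58.6% would become 62-67%.

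Restating design-stage probabilities after termination would leave the estimate, interval, test, thresholds and 10% error rate as they are. In a study described as non-confirmatory, that is no gain for the analysis. The study report can usefully note that Table 11-1 refers to 36 subjects, define the 4-minute SD, and read any miss from the planned interval.
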